## **10.5 Handling of missing values/censoring/discontinuations**

Patients in the dose-escalation part who are ineligible for the dose-determining set may be replaced if necessary. Patients in the safety expansion part will not be replaced.

As of the date of data-cutoff for the final CSR for the purposes of reporting:

- Time to event data (i.e. PFS) will be censored if no event is observed before the cut-off date or before the start date of a new anti-neoplastic therapy, whichever occurs earlier. The censoring date will be the date of last adequate tumor assessment before either of these two dates. If a PFS event is documented after two or more missing or non-adequate tumor assessments, then the date of PFS will be censored at the date of the last adequate tumor assessment. If a PFS event is observed after a single missing or non-adequate tumor assessment, the actual date of event will be used.
- Continuing events (e.g. adverse events, concomitant therapies, etc.) will be summarized using the data cut-off date as the date of completion, with an indication within listings that the event is continuing.

For patients who discontinue the study with ongoing events, the discontinuation date will be used as the completion date of the event with the appropriate censoring as described in the above paragraph.

The reason for discontinuation from study will be summarized and listed, along with dates of first and last LDK378, duration of exposure to LDK378 and date of discontinuation for each patient.

Other missing data will simply be noted as missing in appropriate tables/listings. The FAS will be used.

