#### End dates

The end dates which are used to calculate ‘time to event’ variables are defined as follows:

- Date of death (during treatment as recorded on the treatment completion page or during follow-up as recorded on the study evaluation completion page or the survival follow-up page).
- Date of progression is the first assessment date at which the overall lesion response was recorded as progressive disease.
- Date of last adequate tumor assessment is the date the last tumor assessment with overall lesion response of CR, PR or SD which was made before an event or a censoring reason occurred. In this case the last tumor evaluation date at that assessment is used. If no post-baseline assessments are available (before an event or a censoring reason occurred) the date of randomization/start of treatment is used.
- Date of next scheduled assessment is the date of the last adequate tumor assessment plus the protocol specified time interval for assessments. This date may be used if back-dating is considered when the event occurred beyond the acceptable time window for the next tumor assessment as per protocol (see [Section 3.2.8](#)).

**Example** (if protocol defined schedule of assessments is 3 months): tumor assessments at baseline - 3 months - 6 months - missing - missing - PD. Date of next scheduled assessment would then correspond to 9 months.

- Date of discontinuation is the date of the end of treatment visit.
- Date of last contact is defined as the last date the patient was known to be alive. This corresponds to the latest date for either the visit date, lab sample date or tumor assessment date. If available, the last known date patient alive from the survival follow-up page is used. If no survival follow-up is available, the date of discontinuation is used as last contact date.

- Date of secondary anti-cancer therapy is defined as the start date of any additional (secondary) antineoplastic therapy or surgery.

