**Table 3-2 Options for event dates used in PFS, TTP, duration of response**

| Situation  | Options for end-date (progression or censoring) 
(1) = default unless specified differently in the protocol or RAP             | Outcome                                      |
|--|---|--|
| A No baseline assessment   | (1) Date of randomization/start of treatment    | Censored                                     |
| B Progression at or before next scheduled assessment   | (1) Date of progression
(2) Date of next scheduled assessment    | Progressed
Progressed                     |
| C1 Progression or death after exactly one missing assessment  | (1) Date of progression (or death)
(2) Date of next scheduled assessment   | Progressed
Progressed                     |
| C2 Progression or death after two or more missing assessments   | (1) Date of last adequate assessment 
(2) Date of next scheduled assessment 
(3) Date of progression (or death) | Censored
Progressed
Progressed         |
| D No progression   | (1) Date of last adequate assessment  | Censored                                     |
| E Treatment discontinuation due to 'Disease progression' without documented progression, i.e. clinical progression based on investigator claim | (1) N/A
(2) Date of discontinuation (visit date at which clinical progression was determined)  | Ignored
Progressed                        |
| F New anticancer therapy given   | (1) Date of last adequate assessment
(2) Date of secondary anti-cancer therapy
(3) Date of secondary anti-cancer therapy
(4) N/A     | Censored
Censored
Event
Ignored     |
| G Deaths due to reason other than deterioration of 'Study indication'  | (1) Date of last adequate assessment  | Censored
(only TTP, duration of response) |

1. Definitions can be found in [Section 3.2.7](#).

2. After the last adequate tumor assessment. "Date of next scheduled assessment" is defined in [Section 3.2.7](#).

3. The rare exception to this is if the patient dies no later than the time of the second scheduled assessment as defined in the protocol in which case this is a PFS event at the date of death.

The primary analysis and the sensitivity analyses must be specified in the protocol. Clearly define if and why options (1) are not used for situations C, E and (if applicable) F.

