Partial or complete responses reported prior to any additional anticancer therapy will be considered for ORR computation irrespective of the number of missed assessments before response. In this section, the 'missing adequate assessment' is defined as assessment not done or assessment with overall lesion response equal to UNK. For the sake of simplicity, the 'missing adequate assessment' will also be referred as 'missing assessment'.

As detailed in Section 14 (Appendix 5 and 6) of the LDK378X2103 protocol, the PFS censoring and event date options depend on the presence and the number of missing tumor assessments. *For example, an event occurring after two or more missing assessments is censored in the analysis of PFS at the last adequate tumor assessment before the event date.*

An exact rule to determine whether there is none, one or two missing assessments is therefore needed. This rule will be based on the distance between the last adequate tumor assessment date and the event date.

If the distance is larger than threshold D_1 or D_2 then the analysis will assume one or two missing assessments, respectively. The threshold D_1 will be defined as the protocol specified interval between the tumor assessments plus the protocol allowed window around the assessments. Similarly, the threshold D_2 is defined as two times the protocol specified interval between the tumor assessments plus the protocol allowed window around the assessments. For example, in this study, the protocol defined schedule of tumor assessment is every 6 weeks for the first six cycles, and each assessment is expected to be performed at the scheduled time point plus or minus 1 week, i.e. the window is 2 weeks, then any distance larger than $D_1 = 6+2 = 8$ weeks means one missing assessment and any distance larger than $D_2 = (2*6) + 2 = 14$ weeks means two missing assessments. Please see protocol 7.1 for the complete schedules for tumor assessments.

The same definition of D_2 will be used to determine the PFS censoring reason. Possible censoring reasons for PFS are:

- 1: Ongoing without event
- 2: Lost to follow-up
- 3: Withdrew consent
- 4: Adequate assessment no longer available
- 5: New cancer therapy added
- 6: Event after ≥ 2 missing tumor assessments

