New cancer therapy used in RECIST calculations include any anti-cancer therapy as recorded in the medication, surgery (diagnostic biopsies are excluded) or radiotherapy CRF pages and includes LDK378 treatment from the extension-treatment phase.

Eligibility per RECIST 1.1 (Non-measurable disease only at baseline)

As specified in Section 14 (Appendix 5) of the LDK378X2103 protocol, the RECIST 1.1 criteria imply that only patients with measurable disease at baseline should be included in the study.

If a patient without measurable disease is enrolled, the intent-to-treat (ITT) principle requires including these patients in the analyses. Hence, analyses will be based on FAS including patients with either measurable or non-measurable disease per RECIST 1.1. Therefore, a rule needs to be specified on how to handle these cases.

As specified in Table 14-8 of Section 14 (Appendix 5) of the LDK378X2103 protocol, overall lesion response can be derived for patients without measurable disease at baseline as follows ([Table 5-2](#)).

Table 5-2 Overall lesion response at each assessment: patients with non-target disease only

Non-target lesions	New Lesions	Overall lesion response
CR	No	CR
Non-CR/Non-PD ¹	No	Non-CR/non-PD
UNK	No	UNK
PD	Yes or No	PD
Any	Yes	PD

¹ In general, the **non-CR/non-PD response** for these patients is considered equivalent to an SD response in endpoint determination.

Eligibility per Cheson criteria.

As specified in Section 14 (Appendix 6) of the LDK378X2103 protocol, Cheson criteria imply that only patients with measurable disease should be included in the study. In particular, patients should have **at least one measurable nodal lesions greater than 20mm in the long axis**. In cases where the patient has no measurable nodal lesions greater than 20mm in the long axis at baseline, then the patient must have at least one measurable extranodal lesion (long and short axes are ≥ 10 mm).

Missing baseline tumor assessment

Since the timing of PD cannot be determined for patients with missing baseline tumor assessment, these patients are censored in the PFS analysis at the start date of treatment. This rule, however, only applies to the 'PD component' of the PFS or DOR assessment.

Patients without baseline tumor assessment who die within D₂ distance from start date of treatment will be counted as having an event in the primary analysis of PFS.

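### SAP 5.4.1 builds D2 by doubling a single scan interval, so it departs from protocol 10.5 where the scan spacing changes; the effect on PFS is minor

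*SAP*

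**What the plan says.** Protocol 10.5 sets the rule by counting assessments. After one missing or inadequate assessment the event stands: "If a PFS event is observed after a single missing or non-adequate tumor assessment, the actual date of event will be used". After two or more, PFS is censored at the last adequate assessment.

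SAP 5.4.1 says that an exact rule is needed to tell none, one and two missing assessments apart, and bases it on the time from the last adequate assessment to the event. D1 is one interval plus the window. D2 is "two times the protocol specified interval between the tumor assessments plus the protocol allowed window around the assessments". The only worked values are for the phase where "the protocol defined schedule of tumor assessment is every 6 weeks for the first six cycles": D1 = 8 and D2 = 14 weeks, with a 2-week window. For later phases the SAP says "Please see protocol 7.1 for the complete schedules for tumor assessments". It gives no later thresholds and does not say which interval applies when the last scan and the event lie on either side of a change in spacing.

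The same D2 "will be used to determine the PFS censoring reason". It also governs deaths without a baseline assessment: those within D2 "distance from start date of treatment will be counted as having an event in the primary analysis of PFS".

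Protocol 7.2.1 and Table 7-1 place scans on Day 15 of C2, C4 and C6, then C10 and C14, then C20, C26 and so on, each within 7 days either side.

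**The concern.** Twice one interval equals the time to the second next scan only if the next two gaps are equal. They are unequal when the last adequate scan is C4 (6 weeks, then 12) or C10 (12, then 18). At those points the distance rule can disagree with the count in protocol 10.5, and an event that the protocol keeps may be censored. SAP Table 4-1 does not list this as a change from the protocol.

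PFS and DOR are secondary, descriptive endpoints. At stake are late Kaplan-Meier estimates. C10 Day 15 falls at month 6.7 and C20 Day 15 at month 13.6 (days 204 and 414, each divided by 30.4375), shortly before the 8- and 14-month estimates that SAP 2.7 asks for.

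**Working it through.** **Inputs.** Cycle length is 21 days (protocol 4.1). Scan visits are from protocol 7.2.1. The window is 2 weeks (SAP 5.4.1).

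**The SAP's own figures.** D1 = 6 + 2 = 8 weeks and D2 = 2 × 6 + 2 = 14 weeks. Both reproduce.

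**Schedule.** Day 15 of cycle x is study day 21(x − 1) + 15: C2 36, C4 78, C6 120, C10 204, C14 288, C20 414, C26 540. Successive gaps from C2 are 6, 6, 12, 12, 18 and 18 weeks. From treatment start (day 1) to C2 is 35 days, or 5 weeks.

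**Phase-specific D2.** For intervals of 6, 12 and 18 weeks: 2 × 6 + 2 = 14, 2 × 12 + 2 = 26, 2 × 18 + 2 = 38 weeks.

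**Check against protocol 10.5.** The range allows both visits to move by up to 7 days.

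| Interval doubled | Last adequate → PD | Missed | Distance, weeks (range) | D2 | D2 rule | Protocol 10.5 |
|---|---|---|---|---|---|---|
| Gap after last adequate scan | C4 → C10 | C6 | 18 (16–20) | 14 | censored | event |
| Gap after last adequate scan | C10 → C20 | C14 | 30 (28–32) | 26 | censored | event |
| Gap before the event | C2 → C10 | C4, C6 | 24 (22–26) | 26 | event | censored |

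Each failure holds over the whole range, because D2 must be exceeded to count as missing. The other scheduled pairs with up to three missed scans agree under these two readings. With no scan missed, both readings are always right.

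**Summed gaps.** D2 = next gap + gap after that + 2 weeks:

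- treatment start: 5 + 6 + 2 = 13
- C2: 6 + 6 + 2 = 14
- C4: 6 + 12 + 2 = 20
- C6: 12 + 12 + 2 = 26
- C10: 12 + 18 + 2 = 32
- C14 or later: 18 + 18 + 2 = 38

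This gives the protocol 10.5 answer for every scheduled pair checked.

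**Size, by simulation.** The documents give no missed-scan rate and no PFS assumption. Assumed: exponential PFS with median 6 or 10 months, visits uniform within their windows, 60,000 patients per scenario. The shifts below are in 14-month PFS, relative to counting missed scans as protocol 10.5 does.

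| Scenario | Median 6 | Median 10 |
|---|---|---|
| No scan missed | 0 | 0 |
| Gap after last scan, 5% missed | +0.8 | +1.1 |
| Gap after last scan, 10% missed | +1.6 (23.8% vs 22.2%) | +2.1 (42.7% vs 40.6%) |
| Gap after last scan, 20% missed | +3.1 | +3.5 |
| As 10%, half of progressions scanned early | +0.9 | +1.2 |
| As 10%, half of missed scans made up 8–28 days late | +0.7 | +1.1 |
| Gap before the event, 10% missed | −0.1 | −0.1 |

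Under the first reading at 10% missed, 4.3% and 3.7% of patients are wrongly censored, about one in 25. The binomial standard error with 25 patients is √(0.225 × 0.775 / 25) = 8.4 points and √(0.407 × 0.593 / 25) = 9.8 points.

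**The case against.** The SAP handles most of this. It confines 8 and 14 weeks to the first six cycles and sends the programmer to the full schedule, so only the choice of gap at two changes is left open. D2 can also be read as a distance approximation to the count, in a single-arm phase 1 study where protocol 10.7.3 offers Kaplan-Meier analyses only if numbers allow. The size depends on assumed missed-scan rates.

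This argument settles the size but not the existence of the error. The pointer supplies the schedule, yet neither choice of gap makes the formula agree with protocol 10.5. The SAP presents the rule as exact. The nearest guidance, in protocol Appendix 5 section 3.2.7, looks forward from the last scan ("the date of the last adequate tumor assessment plus the protocol specified time interval for assessments"). It serves back-dating and does not define D2, so it favours the first reading without settling the matter.

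Two stronger readings are tempting. First, a reader might infer that 14 weeks applies throughout, especially as SAP Table 4-1 describes the schedule simply as 6-weekly. On-time progressions at C20 would then be censored (18 > 14 weeks), and late PFS would rise much more. The documents do not support this: SAP 5.4.1 limits the worked values to the first six cycles and refers to the protocol for the rest. Second, a reader might infer that D1 is also at fault. D1 changes no PFS result, because under protocol 10.5 and Appendix 5 Table 3-2 (row C1, default option) an event after one missing assessment keeps its own date.

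**Conclusion.** The D2 rule is wrong as written and its effect is minor. It misclassifies C4 → C10 and C10 → C20 with one missed scan, or C2 → C10 with two, depending on the interval chosen. That part follows from the documents alone.

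The size rests on assumptions. With every scan done there is no effect. With 10% missed and median PFS of 6 to 10 months, 14-month PFS is overstated by about 1 to 2 points under the forward reading and hardly moves under the other. Early or made-up scans reduce the shift. It is well inside the sampling error of a group of 25. Missing here includes assessments rated unknown, so the relevant rate covers more than skipped visits. The reason to correct it is agreement with protocol 10.5, not a material change in results.

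**What to change.** Replace the D2 formula with the sum of the next two scheduled gaps after the last adequate assessment plus 2 weeks, tabulated by last scheduled scan: treatment start 13, C2 14, C4 20, C6 26, C10 32, C14 or later 38 weeks. Alternatively, count a scheduled assessment as missed only once its 7-day window has closed. The two agree for scheduled scans, and the count also covers an unscheduled last adequate scan, for which the table has no row. Use one rule for PFS, DOR and the PFS censoring reasons.

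Apply the scan schedule of the protocol version in force for each patient. Amendment 5 reduced scanning after Cycle 14, and the documents reviewed do not give the earlier spacing.

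Separately, reconcile the limit for deaths without a baseline assessment. Protocol Appendix 5 Table 3-2, note 3, counts such a death as an event "if the patient dies no later than the time of the second scheduled assessment as defined in the protocol". That is C4 Day 15, day 78, or 11 weeks from start (12 with the window). The SAP's 14 weeks runs to day 1 + 98 = 99. The treatment-start value of 13 weeks does not match the note either, so the SAP should state its limit explicitly.

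The cost is one SAP paragraph, a short look-up or count in the PFS/DOR program, one sentence on the death rule, and a check of the earlier protocol version for patients past Cycle 14 before Amendment 5.

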#### **6.4.1.5 Palliative radiotherapy and surgery**

Local radiotherapy for analgesic purposes, or for lytic lesions at risk of fracture may be carried out if required. If palliative radiotherapy is initiated after start of study treatment, the reason for its use must be clearly documented and progression as per RECIST 1.1 must be assessed and documented.

Patients who develop progressive disease but are still deriving clinical benefit from ceritinib therapy, as determined by the Investigator may undergo radiotherapy and/or surgical resection as palliative localized therapy to treat metastatic lesions. Ceritinib should be held for at least 4 days prior to radiotherapy and at least 1 day prior to any surgery. Ceritinib may be resumed  $\geq 3$  days after completing radiotherapy or minor surgery, and  $\geq 2$  weeks after major surgery.

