### 3.2.5 Duration of response

The analysis of the following variables should be performed with much caution when restricted to responders since treatment bias could have been introduced. There have been reports where a treatment with a significantly higher response rate had a significantly shorter duration of response but where this probably primarily reflected selection bias which is explained as follows: It is postulated that there are two groups of patients: a good risk group and a poor risk group. Good risk patients tend to get into response readily (and relatively quickly) and tend to remain in response after they have a response. Poor risk patients tend to be difficult to achieve a response, may have a longer time to respond, and tend to relapse quickly when they do respond. Potent agents induce a response in both good risk and poor risk patients. Less potent agents induce a response mainly in good risk patients only. This is described in more detail by [Morgan \(1988\)](#).

It is recommended that an analysis of all patients (both responders and non-responders) be performed whether or not a “responders only” descriptive analysis is presented. An analysis of responders should only be performed to provide descriptive statistics and even then interpreted with caution by evaluating the results in the context of the observed response rates. If an inferential comparison between treatments is required this should only be performed on all patients (i.e. not restricting to “responders” only) using appropriate statistical methods such as the techniques described in [Ellis et al \(2008\)](#). It should also be stated in the protocol if duration of response is to be calculated in addition for unconfirmed response.

For summary statistics on “responders” only the following definitions are appropriate. (Specific definitions for an all-patient analysis of these endpoints are not appropriate since the status of patients throughout the study is usually taken into account in the analysis).

**Duration of overall response (CR or PR):** For patients with a CR or PR (which may have to be confirmed) the start date is the date of first documented response (CR or PR) and the end date and censoring is defined the same as that for time to progression.

The following two durations might be calculated in addition for a large Phase III study in which a reasonable number of responders is seen.

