If the observed ORR is equal to or greater than 30%, then this will be considered as preliminary evidence of substantial antitumor activity of LDK378 in ALK activated neuroblastoma. If the observed ORR is between 20% and 30% then this will be considered as evidence of moderate antitumor activity, and as limited antitumor activity if it is between 10% and 20%. If the observed ORR is less than 10% (i.e. ≤ 2 CR or PR out of 25), then insufficient antitumor activity will be declared.

Note that for a sample size of $n = 25$ (see section 10.8), if the observed ORR is greater than or equal to 20% (i.e. ≥ 5 CR or PR), then the true ORR has a posterior risk of less than 10% of being in the insufficient antitumor activity category.

A minimally informative unimodal Beta prior distribution of the true ORR is derived as follows. A priori it is assumed that the true mean of the ORR equals 20%. A true ORR of 20% is the midpoint between limited and moderate antitumor activity and serves as a compromise between a skeptical view assuming the treatment has only limited antitumor activity and an optimistic view assuming the treatment has moderate antitumor activity. The parameters of the minimally informative Beta prior distribution of the ORR are then derived as $a=1/4$ and $b=1$.

Best Overall Response

Best overall response (BOR) is the best response recorded from the start of the treatment until disease progression. Patients with a BOR of 'UNKNOWN' will be treated as non-responders when estimating ORR. If any non-palliative cancer therapy is taken while on study any subsequent assessments will be excluded from the BOR determination. MIBG response score per curie criteria will be recorded and listed for patients with neuroblastoma who had MIBG scan.

Determination of BOR per RECIST 1.1

ORR is defined as the proportion of patients with a best overall complete response (CR) or partial response (PR) per RECIST 1.1.

For patients with the primary diagnosis other than lymphoma, BOR will be based on the overall lesion assessment per RECIST 1.1. The evaluation of overall lesion response at each assessment is a composite of the target lesion response, non-target lesion response and presence of new lesions (for details see Protocol Appendix 5).

The BOR for each patient is determined from the sequence of overall (lesion) responses according to the following rules:

- CR = at least two determinations of CR at least 4 weeks apart before progression

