2.7 Analysis of other secondary efficacy objectives

Progression-free survival

PFS is defined as the time from the start date of study drug to the date of the first radiologically documented PD or death due to any cause per RECIST 1.1, for patients with solid tumor; and from the start date of study drug to the date of the first PD as overall disease response or death due to any cause per Cheson, for patients with lymphoma.

If a patient has not progressed or is not known to have died at the date of analysis cut-off or has received any further anticancer therapy, PFS will be censored at the date of the last adequate tumor evaluation before the cut-off date or before the start of the new anticancer therapy date, whichever is earlier. Clinical deterioration will not be considered as a qualifying event for progression.

In particular, PFS will be censored at the last adequate tumor assessment if one of the following occurs:

- 1: Ongoing without event
- 2: Lost to follow-up

- 3: Withdrew consent
- 4: Adequate assessment no longer available
- 5: Initiation of new cancer therapy prior to progression
- 6: Event after ≥ 2 missing tumor assessments

PFS will be described in tabular and graphical format for patients treated at MTD/RDE by expansion (disease) group, and also by indication and by treatment group using Kaplan-Meier methods as described for DOR, including estimated median (in months) with 95% CI, 25th and 75th percentiles and Kaplan-Meier estimated probabilities with corresponding 95% CIs at several time points (including at least 2, 4, 6, 8, 10, 14 months). Censoring reasons will also be summarized. Also duration between treatment start date and cut-off date, and PFS follow-up time will be summarized by expansion, and also by indication and by treatment group.

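### SAP 2.6 and 5.4.1 define disqualifying cancer therapy differently, so a responder counted after palliative radiotherapy can have PFS and DOR censored before the response begins

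*SAP*

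**What the plan says.** - **BOR and ORR.** SAP 2.6: "If any non-palliative cancer therapy is taken while on study any subsequent assessments will be excluded from the BOR determination". Assessments after palliative therapy therefore still count.
- **New cancer therapy.** SAP 5.4.1: "New cancer therapy used in RECIST calculations include any anti-cancer therapy as recorded in the medication, surgery". The radiotherapy pages are named as well. Biopsies are the only exemption; palliative treatment is not mentioned.
- **PFS.** SAP 2.7, where the earlier of data cut-off and start of new treatment decides: "PFS will be censored at the date of the last adequate tumor evaluation before the cut-off date or before the start of the new anticancer". SAP 5.4.1 lists the matching PFS censoring reason as "5: New cancer therapy added".
- **DOR.** SAP 2.6 gives the start and the event but no censoring rule. SAP 5.4 refers to protocol Appendix 5. There, Section 3.2.5 states that "the end date and censoring is defined the same as that for time to progression", and Table 3-2 (situation F, covering PFS, TTP and DOR) defaults to the last adequate assessment before new therapy.
- **What is allowed on treatment.** Protocol 6.4.1.5: "Local radiotherapy for analgesic purposes, or for lytic lesions at risk of fracture may be carried out if required". Progression is not a precondition, but it must be assessed and documented when palliative radiotherapy starts on study.
- **A further ORR sentence.** SAP 5.4.1: "Partial or complete responses reported prior to any additional anticancer therapy will be considered for ORR computation", regardless of how many assessments were missed beforehand.

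**The concern.** Response and its duration should rest on the same stretch of follow-up. Here one patient can be inside the observation window for ORR and outside it for PFS and DOR. Three things follow.

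- A programmer who meets such a patient has no rule to follow and must drop, truncate or improvise the DOR value.
- PFS is cut without progression in patients irradiated for pain or fracture risk. That censoring is plausibly informative.
- If the broad definition in 5.4.1 is taken to govern response as well, because it speaks of RECIST calculations generally, the same patient is a responder under 2.6 and a non-responder under 5.4.1. The neuroblastoma group is judged on fixed ORR cut-offs, so who counts as a responder matters.

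**Working it through.** **Plan's own figures.** No stated figure concerns DOR censoring. The figures that depend on who is a responder are those for the Group 1 rule (at least 5 responses in 25). Exact binomial gives 9.80% at a true ORR of 10% and 90.95% at 30%, against 9.8% and 91.0% stated. With the SAP's Beta(1/4, 1) prior, 5 responses in 25 give Beta(5.25, 21), whose 80% interval is 10.7% to 30.3%, as stated.

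**Inputs for the date check.**
- Schedule (protocol 7.2.1, 21-day cycles): Day 15 of cycle c is study day 21(c − 1) + 15. Cycles 2, 4, 6 and 10 give Days 36, 78, 120 and 204.
- Confirmation (SAP 2.6): two determinations at least 4 weeks apart. Days 78 and 120 are 42 days apart.
- Duration (Appendix 5, Section 4.5.1): end − start + 1. The same section says time-to-event values can never be negative.

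**Illustrative patient (assumed).** SD on Day 36; palliative radiotherapy on Day 50 without PD, recorded on a page that 5.4.1 uses; PR on Days 78, 120 and 204; no PD.

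| Rule applied | BOR | PFS | DOR |
|---|---|---|---|
| As written: 2.6 for BOR, 5.4.1 for censoring | PR, counted in ORR | censored Day 36 | 36 − 78 + 1 = −41 days |
| Palliative therapy exempt for all endpoints | PR, counted in ORR | censored Day 204 | 204 − 78 + 1 = 127 days, censored |
| Any therapy counts for all endpoints | SD, not a responder | censored Day 36 | none |

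Either uniform rule gives a coherent answer; the mixture does not.

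**How general this is.** If the censoring day c falls before the response day s, then c − s + 1 is at most 0. The fault therefore arises whenever radiotherapy precedes the first response and no PD is documented. It does not arise when radiotherapy follows the first response: radiotherapy on Day 90 in a patient with PR on Day 78 gives 78 − 78 + 1 = 1 day, censored. That is short but possible.

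**Consequence for ORR.** Suppose one of five responders first responded after palliative radiotherapy. Counting that patient gives 5/25 = 20%, which SAP 2.6 calls moderate activity. Not counting the patient gives 4/25 = 16%, limited activity. The posterior probability that the ORR is below 10% is 7.9% under Beta(5.25, 21) and 19.8% under Beta(4.25, 22).

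**Against the protocol.** Appendix 5, Section 3.1 ordinarily excludes assessments after any alternative cancer therapy, with no palliative exception. The exception in SAP 2.6 departs from that, but SAP Table 4-1 lists only two other BOR changes. For lymphoma, Appendix 6, Section 4.1 ends best response at new anticancer therapy, also without the exception.

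**The case against.** The strongest reply is that the collision may never occur. Protocol 6.4.2.1 exempts palliative radiotherapy from its ban on other anticancer therapy, which could be read as placing it outside that term. SAP 2.4.2 records on-study non-drug therapies on the concomitant medication page and discusses antineoplastic radiotherapy under therapies begun after discontinuation. SAP 5.6.4 has date rules only for prior and post therapies. If the pages named in 5.4.1 hold no on-treatment palliative radiotherapy, the two rules agree in practice. This stands as a possibility: the CRF is not in the documents and 5.4.1 does not say so. The bracket in 6.4.2.1 may equally do no more than limit a prohibition.

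Several stronger readings are tempting and are not supported.

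- A reader might infer that SAP 5.4.1 itself censors DOR. Its list of reasons is for PFS; the DOR rule comes only through protocol Appendix 5.
- A reader might infer that 5.4.1 restricts ORR to responses before any additional therapy. That sentence is mainly about missed assessments and does not expressly exclude later responses. It also cannot both restrict ORR and leave the example patient a responder.
- A reader might infer that very early radiotherapy would send PFS censoring back to Day 1. Protocol 6.4.1.5 requires progression to be assessed when the radiotherapy starts, so Day 1 is not the expected case. If that assessment shows PD, PFS is an event, later responses do not count, and the problem disappears. If it is adequate, shows no PD and precedes the radiotherapy, censoring moves to about that date. In the example that is near Day 50, still before Day 78.

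It is also fair to say that exempting palliative therapy everywhere is not clearly the better direction, since it could credit shrinkage produced by irradiation.

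**Conclusion.** The inconsistency is on the page and should be corrected. BOR/ORR ignores palliative therapy, whereas PFS censoring, and DOR censoring through Appendix 5, uses any anti-cancer therapy on the named pages. An impossible DOR needs three conditions: the radiotherapy is recorded on one of those pages, it is given without PD, and it precedes the first response. Under them the example yields −41 days for a patient counted in ORR. If 5.4.1 is read to cover BOR as well, it contradicts 2.6 directly, so that reading does not rescue the text.

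The documents do not show that any DOR in this trial is in fact zero or negative. The number of affected patients and the CRF page are not given, and the endpoints are secondary and descriptive in a single-arm phase 1 study. One affected patient could move the neuroblastoma group between activity categories only if the count sits at a cut-off.

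**What to change.** - Use one definition of new anticancer therapy for BOR/ORR, PFS and DOR in SAP 2.6, 2.7 and 5.4.1, and name the CRF pages that feed it.
- State the DOR censoring rule in the SAP.
- If the non-palliative exception is kept, list it in Table 4-1 as a departure from Appendix 5, Section 3.1, and do not credit response in an irradiated target lesion.
- Run the other definition for all three endpoints together as a sensitivity analysis.

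The cost is SAP wording, a flag for palliative intent and one extra analysis.
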